#### LIST OF ABBREVIATIONS

AE Adverse Events

ADC Apparent diffusion coefficient

AUC Area under the curve AS Active Surveillance

DCE Dynamic contrast enhanced DWI Diffusion-weighted imaging

EPI Echo-planar imaging

HIFU High-intensity focused ultrasound

hrMRI High resolution MRI
mpMRI Multiparametric MRI
MR/US MRI-ultrasound

MRI Magnetic resonance imaging PET Positron emission tomography

PI-RAD Prostate Imaging-Reporting and Data System

PSA Prostate specific antigen

[figure not shown]
PSMA Prostate specific membrane antigen

ROI Region of interest

SAE Serious Adverse Events UTI Urinary Tract Infection

# STUDY SCHEMA

High-Resolution, 18F-PSMA PET-MRI for Mapping Prostate Cancer in Patients Considering Focal High-Intensity Focused Ultrasound (HIFU) Therapy

# **STUDY SUMMARY**

Title	High-Resolution, 18F-PSMA PET-MRI for Mapping Prostate Cancer in Patients Considering Focal High-Intensity Focused Ultrasound (HIFU) Therapy or Radical Prostatectomy
Short Title	High resolution PET-MRI before prostate cancer HIFU or radical prostatectomy
Protocol Number	Pro00000832
Phase	Two parts: Phase II and Pilot
Methodology	Single arm, paired imaging (Phase II)
Study Duration	3 years
Study Center(s)	Cedars Sinai Medical Center
Objectives	Phase II Study (HIFU): Primary Endpoint: Number of additional biopsy-proven cancers that novel imaging modalities of hrMRI and/or F18-PSMA PET would detect when compared to reference standard imaging of mpMRI in patients undergoing HIFU procedure. Secondary Endpoint: Negative biopsy rate of standard 12-core biopsy 6 months following HIFU therapy.  Phase II Study (Radical Prostatectomy(RP)): Primary Endpoint: To determine the sensitivity in detection of prostatic carcinoma of novel imaging modalities of hrMRI and /or F18-PSMA PET compared to reference standard mpMRI in patients scheduled to undergo radical prostatectomy. Secondary Endpoint: Specificity of hrMRI, F18PSMA PET and mpMRI for detecting all tumors and metastasis at 6 months follow up.
Number of Subjects	30 Study Subjects (Phase II HIFU), 31 Study Subjects (Phase II RP)

Diagnosis and Main Inclusion Criteria	
 
Diagnosis for Pilot trial: Any patient scheduled to undergo radical prostatectomy Diagnosis: Clinically localized, unilateral, high-grade prostate cancer OR at high risk for having unrecognized high grade Prostate Cancer Inclusion Criteria:         
 
Biopsy consisting of ≥ 10 tissue cores sampled
 
PSA ≤20 ng/mL
 
cT1-cT2c
 
Either overall Gleason score ≥ 7 with Gleason grade 4 or 5 component localized to one lobe (i.e. right or left) OR overall Gleason score 6 with ≥ half of systematic biopsy cores positive and ≥ 50% of core involvement in at least one core
 
Patients considering focal HIFU therapy
 
Patients considering radical prostatectomy
 
 
 
		
Study Imaging	F18-PSMA PET-MRI in combination with multiparametric prostate MRI using high resolution DWI		
Control Imaging	Standard multiparametric prostate MRI		
Reference standard	MRI-targeted prostate biopsies will serve as the reference standard and all lesions seen on any MRI protocol will be biopsied. In the pilot trial, the prostatectomy pathology will serve as the reference standard.		
Statistical analysis	Our hypothesis is that 20% of biopsy-proven tumors will be detected on PET-hrMRI and not on standard MRI. If we assume that no biopsy proven tumors will only be detected on standard MRI, at alpha=0.05, n=40 provides a power of at least 90% when we account for 5 cases that will not be evaluable. The RP phase II study is a parallel study arm using PSMA-PET imaging for intraprostatic cancer detection, but using radical prostatectomy pathology as the gold standard. The radical prostatectomy pilot arm will allow us to compensate for limitations and describe this data in parallel with the HIFU analysis.		

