We herein propose a prospective trial to evaluate the effectiveness of F18-PSMA PET-hrMRI versus standard mpMRI at identifying prostate cancer targets for HIFU therapy. Patients with clinically localized, unilateral high grade prostate cancer (Gleason score 7-10 prostate cancer localized to one lobe on prior biopsies) OR at high risk for having unrecognized high grade prostate cancer (overall Gleason score 6 with ≥ half of systematic biopsy cores positive and ≥ 50% of core involvement in at least one core), interested in HIFU would receive both a standard mpMRI and F18-PSMA PET-hrMRI. They would then undergo a mapping biopsy using a standard sextant template plus MRI/US-fusion targeted biopsy of any suspicious lesion on mpMRI or PET-hrMRI. The primary endpoint would assess the number of biopsy-proven cancers that mpMRI would have missed compared with PET-hrMRI. Following our tumor mapping study, patients with high grade disease (i.e. Gleason grade 4 or 5) in one lobe undergo hemigland or focal HIFU of that lobe. At 6 months, patients would undergo repeat prostate biopsy to assess the negative biopsy rate in the treated region and absence of Gleason grade 4 or 5 in the untreated region as secondary endpoints.

Tumors invisible on MRI tend to be small, low-grade tumors that do not require treatment. However, it may be important to identify these tumors for future surveillance. An important limitation of this phase II study is that it will not be able to define the sensitive of imaging for these low-grade tumors. Therefore, a pilot study is included in which patients scheduled to undergo radical prostatectomy will have a preoperative PET-hrMRI. The prostatectomy pathology will be the reference standard. Since the true location of all tumors will be known, both the sensitivity and specificity of PSMA-PET MRI can be determined

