# 2.9 PET-hrMRI prior to prostatectomy

An important limitation of studying a new imaging modality in patients undergoing HIFU is that tumors are identified by biopsy, which is susceptible to sampling error. In other words, tumors invisible on MRI and missed on systematic prostate biopsy are not considered in

defining the limitation of our novel imaging. These tumors are expected to be small, low grade tumors that do not require treatment. However, future research will need to consider appropriate surveillance strategies for these MRI-invisible tumors. To define sensitive of PET-hrMRI, we would need to know where all the tumors are. Therefore, a pilot study is included in which patients scheduled to undergo radical prostatectomy will have a preoperative PET-hrMRI. The prostatectomy pathology will be the reference standard. Since the true location of all tumors will be known, both the sensitivity and specificity of PSMA-PET MRI can be determined.

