## Mapping Biopsy Protocols

After the pre-HIFU imaging protocol for tumor mapping, all patients will undergo a transrectal ultrasound-guided targeted mapping biopsy. The biopsy will include a standard sextant template plus MR/US-fusion targeted biopsy of any lesions with PI-RADS scores ≥3 on hrMRI or F18-PSMA PET positivity. These areas will be targeted using the UroNav targeting software platform. We use the UroNav platform for performing MR-PET-US fusion biopsies. It is an FDA approved, commercially available platform. Uronav received 510(k) clearance from the FDA and it is a commercially available platform, link to document:

https://www.accessdata.fda.gov/cdrh docs/pdf15/K153073.pdf. As an exploratory analysis, remnant formalin-fixed paraffin embedded tumor tissue will be requested for RNAseq transcriptome analysis of lesions that are positive on mapping biopsy.

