#### 6.0 STATISTICAL ANALYSIS

# 6.1 HIFU Phase II Study

Our preliminary data suggests that up to 60% of tumors invisible to standard mpMRI are detected on hrMRI in an active surveillance population. It is unclear how many additional lesions will be identified on PSMA PET-MRI. Since all areas of concern will be biopsied and only biopsy-proven tumors will be treated with HIFU, the morbidity of the surgical intervention is minimized and its potential to achieve cure is maximized.

Power Assessment: The main hypothesis to be tested is whether the sensitivity of PSMA PET-hrMRI is greater than mpMRI alone in 20% considering the prostate divided in 6 sections for each patient. The power is evaluated using 1000 simulations based on the McNemar's type test proposed by Yang et al. (17,2010). Data is generated based on four correlations: r1: between lesions evaluated by PSMA PET-hrMRI for the same patient, r2: between lesions evaluated by mpMRI for the same patient, r3: between evaluations PSMA PET-hrMRI and mpMRI for the same lesion and r4: between evaluations PSMA PET-hrMRI and mpMRI for the different lesions at the same patient. Based on preliminary data, we estimated mpMRI sensitivity of 42%, (r1, r2, r3, r4) = (-0.249, -0.119, 0.714, -0.172) using Spearman correlation, average number of lesions of 2.5 per patient and prevalence of patients with at least one positive biopsy section equal to 82%. The results are presented in Table 1.

**Table 1.** Power for McNemar test proposed by Yang et al. (2010) to detect a difference of 20% between sensitivities of the combination (PET-hrMRI or mpMRI) and mpMRI

Total Sample # Patients with at least one positive biopsy
Size section Power

20	16	70.2
25	21	81.5
30	25	88.9
35	29	93.1
40	33	95.5

The minimum sample size to reach at least 85% of power is 30 patients with complete imaging data. Patients with incomplete imaging data will be replaced.

Statistical Analysis: Sensitivities will be compared using McNemar's type test proposed by Yang et al. (17,2010). for cluster matched binary data. In addition, the 95% confidence interval for difference between sensitivities will be calculated as proposed by Yang et al. (18,2012).

Secondary Endpoints: Negative biopsy rate within treatment zones on standard 12-core biopsy 6 months following HIFU therapy; rate of high grade cancer in the untreated lobe.

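### HIFU cohort: the Summary's reference-standard row omits the systematic sextant cores, which conflicts with the body and, taken literally, fixes the combination's sensitivity at 100%

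*Combined protocol and SAP*

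**What the plan says.** The Study Summary's reference-standard row reads "MRI-targeted prostate biopsies will serve as the reference standard and all lesions seen on any MRI protocol will be biopsied". For the other cohort it continues: "In the pilot trial, the prostatectomy pathology will serve as the reference standard". The row is the only place that says which biopsies form the HIFU reference. Section 6.2 merely calls that cohort's gold standard biopsy-based, and 6.1 does not say which cores make a section positive.

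The rest of the protocol describes a wider biopsy:

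- Section 1.0: "They would then undergo a mapping biopsy using a standard sextant template plus MRI/US-fusion targeted biopsy of any suspicious lesion on mpMRI or PET-hrMRI".
- Mapping Biopsy Protocols (3.4.3): "The biopsy will include a standard sextant template plus MR/US-fusion targeted biopsy". Section 3.1 and the HIFU calendar in 3.4.2 agree.
- Section 2.9, on the limits of the biopsy reference: "tumors invisible on MRI and missed on systematic prostate biopsy are not considered". Both conditions must hold, so a cancer that imaging misses but a systematic core finds is counted.
- Section 6.1 plans the comparison "considering the prostate divided in 6 sections for each patient", with mpMRI sensitivity 42% and, in the caption of Table 1, a 20-point difference between the combination (PET-hrMRI or mpMRI) and mpMRI.

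**The concern.** A targeted core exists only where a scan was called suspicious. If targeted cores define the reference, every reference-positive cancer was seen by at least one scan, and cancers found only on the sextant template drop out of the denominator. The combination is then 100% sensitive whatever the quality of the imaging, and mpMRI is flattered as well.

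That cannot be squared with Table 1, where 62% for the combination means that 38% of reference-positive cancers are seen by no scan. An analyst who looks for the definition finds only the Summary's. If the choice stays open, it can be made after the data are seen, and the same patients could yield 62% or 100%.

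**Working it through.** **Inputs.** From 6.1: mpMRI sensitivity 42%; difference 20 points; same-lesion correlation r3 = 0.714; 82% of patients with a positive section; Table 1 power 88.9% at 30 patients. From the Study Summary: alpha 0.05, and no tumor seen on standard MRI only.

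**The plan's own figures.** 42 + 20 = 62%. 30 × 0.82 = 24.6, which matches the 25 positive patients in Table 1. The 88.9% was not reproduced exactly. Simulations (5,000 replicates, two-sided 0.05, a clustered McNemar-type statistic as a stand-in for the cited test, correlations placed on a latent normal scale, 62% assigned to PET-hrMRI alone) gave 85.1% to 92.6% for 25 patients, depending on the lesion-count distribution. With mpMRI nested inside a 62% combination they gave 99.6%. The lesion-count distribution, sidedness and correlation scale are not stated, so this mismatch is not evidence of an error. It does leave unsettled whether 62% was simulated for the combination, as the caption says, or for PET-hrMRI alone, as the text of 6.1 can be read. Both are worked below.

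**Assumptions.** The 42% and 62% were measured against a reference that includes systematic cores, and lesions seen only on mpMRI are targeted, as the Summary row says.

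**Reading A: 62% is the combination (Table 1 caption).** Of 100 reference-positive cancers, mpMRI sees 42, the new imaging adds 20, and no scan sees 38. A targeted-only reference drops the 38:

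- mpMRI: 42/62 = 67.7%
- combination: 62/62 = 100%
- gain: 20/62 = 32.3 points, instead of 20

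**Reading B: 62% is PET-hrMRI alone, with r3 = 0.714 as a latent normal correlation.**

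- Seen by both: Φ₂(z₀.₄₂, z₀.₆₂; 0.714) = 37.3%
- Seen on mpMRI only: 42 − 37.3 = 4.7%
- Seen by either: 62 + 4.7 = 66.7%

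| | All cores | Targeted cores only |
|---|---|---|
| mpMRI | 42% | 42/66.7 = 63.0% |
| PET-hrMRI alone | 62% | 62/66.7 = 92.9% |
| Combination | 66.7% | 100% |
| Gain, PET-hrMRI alone | 20 | 20/66.7 = 30.0 |
| Gain, combination | 66.7 − 42 = 24.7 | 100 − 63.0 = 37.0 |

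**What does not move.** A cancer missed by every scan adds nothing to the number of additional cancers. It is also a concordant pair, so it does not enter a McNemar-type statistic built on discordant pairs. Simulated power for PET-hrMRI against mpMRI under reading B, with 2 or 3 lesions per patient, was 86.6% with all cores and 86.3% with targeted cores only, which is simulation noise. The denominators of the sensitivities, of their difference and of its confidence interval do change.

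**The case against.** The strongest reply is that the row is merely shorter than the body. It does not say that targeted cores are the only reference; sextant cores are prescribed throughout; 2.9 counts what they find; and 6.1 plans for less than 100%. This stands. A reader might infer that 100% sensitivity is built into the trial, and the documents do not support that. They support a conflict between the one explicit definition and everything around it.

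The endpoint in 3.3 is a number of additional cancers, which the choice does not touch. This also stands, but 6.1 reports sensitivities and a confidence interval for their difference, and those are touched.

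The size depends on how the preliminary 42% was obtained, which is not stated. Had it been measured on targeted cores only, the combination would be 100% and the gain 58 points, which does not match the planned 20 either. The Summary states its own hypothesis as 20% of biopsy-proven tumors; on a targeted-only reference with nothing seen on mpMRI only, that stays 20 points (mpMRI 80%, combination 100%). So the inflation applies to the 42% and 62% behind Table 1, not to every statement of the hypothesis.

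A reader might also take r3 = 0.714 as proof that the preliminary reference included cancers missed by all imaging. It proves nothing: the largest binary correlation possible at 42% and 62% is (0.42 − 0.42 × 0.62)/√(0.42 × 0.58 × 0.62 × 0.38) = 0.666, so 0.714 cannot be a binary correlation at these margins under any reference.

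Finally, the protocol discloses the limits of a biopsy reference and adds the prostatectomy cohort because of them. That cohort uses whole-gland pathology and is outside this point.

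**Conclusion.** The point holds for the HIFU cohort as an inconsistency in the definition of the reference standard. Applied literally, the Summary's rule makes the combination 100% sensitive by construction. If the planning values rest on a reference that includes systematic cores, the combination's gain becomes 32.3 points instead of 20 (62% as the combination), or 37.0 instead of 24.7 (62% as PET-hrMRI alone, latent correlation 0.714). In the second case PET-hrMRI alone gains 30.0 instead of 20. The gains of the combination and of PET-hrMRI alone answer different questions and should not be merged into one range.

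The count of additional cancers and the McNemar-type test stand. The sensitivities, the difference and its 95% confidence interval depend on the rule. If systematic cores count, as the body implies, 62% against 42% stands as planned.

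**What to change.** 1. In the Study Summary, reword the row for the HIFU cohort: *the reference standard is all mapping-biopsy cores, systematic sextant and targeted; a section is positive if any core in it is positive.*
2. In 6.1 add: *cancers found only on systematic cores remain in the sensitivity denominator and count as missed by both modalities.*

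This is two sentences, with no new procedures or patients. The cost is that the reported sensitivities are less favourable than under a targeted-only rule. A milder bias remains, because imaging-positive areas still receive extra cores; it should be named when the results are reported.

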#### 1.0 STUDY ABSTRACT

The arrival of High-Intensity Focused Ultrasound (HIFU) technology along with advances in prostate imaging may make focal gland ablation feasible. While the mainstays of therapy for clinically localized prostate cancer, surgery and radiation therapy, induce significant morbidity such as urinary incontinence, erectile dysfunction, and bowel dysfunction due to bystander effects of whole-gland treatment, HIFU permits focal destruction of prostate cancers, which has the potential to minimize these morbidities and maximize quality of life. Advances in prostate MRI allow the majority of high grade cancers to be detected. Software platforms exist that enable real-time fusion of prostate MRI images with ultrasound, which allows for targeting of prostate lesions found on MRI during transrectal biopsy. The confluence of all of this technology—HIFU, multiparametric MRI (mpMRI), and MR/US-fusion targeting—creates the possibility of highly targeted focal ablation of prostate cancers. Nonrandomized clinical trials of hemigland and focal ablation with HIFU in Europe have shown promising trifecta rates—cancer control, potency, & continence—up to 1y post-treatment.

While early results of HIFU therapy for clinically localized prostate cancer are promising, the effectiveness of HIFU therapy will ultimately be limited by the accuracy of prostate cancer imaging. Because prostate cancer is often multifocal, identification of all clinically relevant prostate cancer lesions is critical to complete treatment of the disease, whether it is hemigland or true focal ablation. Modern mpMRI is unable to detect 20% of high-grade cancer and approximately 50% of low-grade cancers. To address this shortcoming, our team at Cedars-Sinai has developed high-resolution prostate MRI (hrMRI) technology that improves resolution 5-fold compared with standard multiparametric MRI. (1) High-resolution imaging has been shown to detect 60% of tumors not seen on standard MRI.(2) Pairing this technology with PET may allow highly specific targeting for focal therapy. Because the oncological effectiveness of focal therapy depends on robust targeting, PET-hrMRI could provide a significant advantage in cancer control outcomes for HIFU.

We herein propose a prospective trial to evaluate the effectiveness of F18-PSMA PET-hrMRI versus standard mpMRI at identifying prostate cancer targets for HIFU therapy. Patients with clinically localized, unilateral high grade prostate cancer (Gleason score 7-10 prostate cancer localized to one lobe on prior biopsies) OR at high risk for having unrecognized high grade prostate cancer (overall Gleason score 6 with ≥ half of systematic biopsy cores positive and ≥ 50% of core involvement in at least one core), interested in HIFU would receive both a standard mpMRI and F18-PSMA PET-hrMRI. They would then undergo a mapping biopsy using a standard sextant template plus MRI/US-fusion targeted biopsy of any suspicious lesion on mpMRI or PET-hrMRI. The primary endpoint would assess the number of biopsy-proven cancers that mpMRI would have missed compared with PET-hrMRI. Following our tumor mapping study, patients with high grade disease (i.e. Gleason grade 4 or 5) in one lobe undergo hemigland or focal HIFU of that lobe. At 6 months, patients would undergo repeat prostate biopsy to assess the negative biopsy rate in the treated region and absence of Gleason grade 4 or 5 in the untreated region as secondary endpoints.

Tumors invisible on MRI tend to be small, low-grade tumors that do not require treatment. However, it may be important to identify these tumors for future surveillance. An important limitation of this phase II study is that it will not be able to define the sensitive of imaging for these low-grade tumors. Therefore, a pilot study is included in which patients scheduled to undergo radical prostatectomy will have a preoperative PET-hrMRI. The prostatectomy pathology will be the reference standard. Since the true location of all tumors will be known, both the sensitivity and specificity of PSMA-PET MRI can be determined

## 2.0 BACKGROUND AND RATIONALE

### 2.1 Prostate Cancer: Current Standard of Care in Treatment

Prostate cancer is the most common non-cutaneous cancer and the second-leading cause of cancer mortality in American men, accounting for 25% (192,280) of new cancer diagnoses and 9% (27,360) of male cancer deaths(3). Clinically localized prostate cancer accounts for the vast majority of new cancer diagnoses, with an estimated 91% of new cases diagnosed at local or regional stages(3). Traditional treatment options for localized disease vary widely, from watchful waiting or active surveillance to aggressive treatment with surgery, radiation therapy, or brachytherapy. Active surveillance is considered the standard-of-care for low grade (e.g. Gleason score 3+3=6) prostate cancers and even some intermediate risk cancers. On active surveillance, patients with long life expectancy who develop a component of high Gleason grade cancer (i.e. Gleason grade 4 or 5) are recommended to have definitive local therapy such as prostatectomy or radiation. While aggressive therapies such as surgery and radiation do offer the opportunity for cure, they are fraught with side effects that can significantly affect quality of life, including erectile dysfunction, urinary incontinence, and bowel dysfunction (4-7). Even recent advances in robotic surgery and radiation techniques have not appeared to significantly reduce the long-term morbidities of definitive local therapy.

# 2.2 HIFU: Historical Background and FDA Approval

High-Intensity Focused Ultrasound (HIFU) is a noninvasive therapy that precisely delivers ablative ultrasonic energy to deep tissues through skin and mucosa, allowing for transrectal focal ablation of prostate cancers. While the mainstays of therapy for clinically localized prostate cancer induce significant morbidity such as urinary incontinence, erectile dysfunction, and bowel dysfunction due to bystander effects of whole-gland treatment, HIFU permits focal destruction of prostate cancers by ablating either half of the prostate gland or only the tumor itself; these approaches have the potential to minimize morbidities associated with whole-gland treatment and thereby maximize quality of life. HIFU treatment (primarily hemigland and whole-gland) has been used extensively over the last fifteen years in Europe, Canada, and Mexico, and there are numerous articles describing its safety and effectiveness for this application in the Urology literature.

While HIFU therapy has a long track record abroad, it has only recently been approved for prostate ablation in the US. In October 2015, the FDA gave de novo clearance to the Sonablate 450 HIFU platform (manufactured by SonaCare Medical) for the ablation of prostate tissue, making it the first to be approved for this indication in the US. In November 2015, the Ablatherm HIFU platform (manufactured by EDAP TM SA) was given 510(k) clearance for the same indication. While the approvals for these devices do not specifically mention application to prostate cancer, academic and industry leaders are hailing this technology as a major advance for focal prostate therapy, hinting that this technology can avoid the morbidities of surgery for prostate cancer. Local academic centers have already begun to use and market this technology.

